Dose-escalation rules	
Dose escalation decisions will be made by a Dose Escalation Committee (DEC) and will be based on safety and pharmacodynamic evaluations including but not limited to, dose-limiting toxicities, AEs, SAEs, and total IgG levels.
 
Dose-limiting toxicity (DLT) will be defined generally as severe (Grade 3) AEs occurring in <math>\geq 2</math> subjects that are determined to be clinically significant and considered related to study drug.
 
If 2 or more subjects at any time in any cohort (8 total subjects per cohort) have Grade 3 AEs that are determined to be clinically significant and considered to be related to study drug, dosing will be halted within that cohort and dose-escalation to a higher dose will not occur. If the dose-escalation stopping rule is met during Cohort 1 (10 mg/kg) all safety data and all available pharmacodynamics data will be reviewed and the cohort may resume (if applicable) or a new cohort may be added, at a dose at least 50% lower than the 10 mg/kg dose. If the stopping rule is not met in Cohort 1 (10 mg/kg), dose-escalation may proceed up to a maximum of 30 mg/kg. If the dose-escalation stopping rule is met for the first time during Cohort 2, all safety data and all available pharmacodynamics data will be reviewed and the cohort may resume (if applicable) or a new cohort may be added at a dose at least 30% lower than the Cohort 2 dose. If the stopping rule is not met in Cohort 2, dose-escalation may proceed up to a maximum of 45 mg/kg; however, this cohort may also receive a dose equal to or less than 30 mg/kg based on evaluation of all safety and pharmacodynamic data.

Study stopping rule	
If any subject experiences a life-threatening AE (Grade 4) that is considered to be related to study drug, any further dosing in all enrolled subjects will be suspended until the DEC has evaluated the event and determined the next appropriate course of action. At any time during the study, the study may be discontinued if the DEC determines that further drug exposure would pose an undue risk to subjects.

Individual stopping rule	
Dosing for any individual subject will be discontinued (i.e., further treatment with the study drug will not be given) if the subject experiences any study drug-

	related SAE or any study drug-related non-SAE adverse event that, in the judgement of the Investigator (following consultation with the Medical Monitor, if desired) suggest that it could be unsafe to administer further study drug to that subject. Additionally, a subject will be discontinued from further treatment with study drug, at the discretion of the Investigator with consultation with the Medical Monitor, if they require a significant increase in dose(s) of anti-pemphigus medication(s) for the management of pemphigus.
Pharmacokinetics	
The PK of SYNT001 will be evaluated following the first and last (fifth) doses of SYNT001.
 
Starting on Days 0 and 28, serum samples will be collected just prior to the start of study drug infusion (pre-dose), at 5 minutes and 2, 4, 6, 24, and 48 hours after the end-of-study drug infusion. Additional samples will be collected on Days 5 and 33.
 
Study drug concentration will be used to calculate the following PK parameters: <math>t_{1/2}</math>, <math>C_{max}</math>, <math>T_{max}</math>, <math>AUC_{0-24}</math>, and <math>AUC_{0-\infty}</math>.

Pharmacodynamics/ Activity	PD samples will be collected for analysis of IgG (serial assessment of IgG levels to identify $C_{min}$ , $T_{min}$ ); IgG1-4 subtype levels; IgA levels; IgM levels; albumin levels; anti-Dsg (1 and 3) antibody levels; serum AECA by direct immunofluorescence; CIC; C3; exploratory biomarkers ( FCGR2A SNP, RNAseq, urine IgG, $CD3^+CD4^+$ T, $CD3^+CD8^+$ T, monocytes, NK cells and B cells), and additional exploratory analyses to investigate immune response associated with pemphigus.
Immunogenicity	Samples will be collected for immunogenicity analyses on Days 0 (pre-dose), 14, 28, 56, 84 and 112.
Skin biopsy	Optional skin biopsy samples from lesional or non-lesional skin will be collected on Day 0 pre-dose and on Days 1, 2, 14, 33, 56 and 84 to analyze SYNT001 levels.
Photography	Photographs of active lesions will be taken at Day 0. Follow-up photographs of the same areas will be taken on Days 33, 56, 84 and 112. Subjects who begin a steroid taper will have additional photographs taken at the clinic visit during which the decision to begin the taper is made.
Statistical methods	
Sample size consideration
 
Formal sample size calculations were not performed. The number of subjects was chosen based on feasibility and was considered sufficient to meet the study objectives.
 
Data presentations/Descriptive statistics
 
Three populations will be employed in the analysis of study data.

	
 
The intent-to-treat (ITT) population will consist of all subjects who have received at least one dose of study drug. All safety analyses will be performed on the ITT population.
 
The PK population will consist of all subjects who receive at least one dose of study drug and have sufficient post-dose blood samples to obtain PK parameters.
 
The PD population will consist of all subjects who receive at least one dose of study drug and have post-dose PD data available.
 
 
Primary safety analyses will be performed on the ITT population. Demographics, subject disposition, and screening and baseline characteristics will be summarized for the PK and ITT populations, where appropriate.
 
Criteria for evaluation
 
  
 Objective	Endpoint	
   
 Primary	
 
 Safety and tolerability of 5 once-weekly IV infusions of SYNT001 to subjects with pemphigus vulgaris or foliaceus	AEs and clinical (safety) laboratory tests	
 
 Secondary	
 
 PK of SYNT001 following a 1-hour IV infusion	PK parameters: <math>t_{1/2}</math>, <math>C_{max}</math>, <math>T_{max}</math>, <math>AUC_{0-24}</math>, and <math>AUC_{0-\infty}</math>.	
 
 Effect of 5 once-weekly IV doses of SYNT001 on:                     
 
Total IgG (IgG1-4), IgA, IgM, and albumin
 
Serum anti-Dsg (1 and 3) antibodies
 
 	Changes in levels of IgG, IgG subtypes (IgG1-4), IgA, IgM, albumin, serum anti-Dsg (1 and 3) antibodies	
 
 Assess immunogenicity	Anti-SYNT001 antibodies	
 
 Disease Activity	PDAI Scores	
 
 Exploratory	
 
 Effect of 5 once-weekly IV doses of SYNT001 on biomarkers including:                     
 
CIC
 
C3
 
Serum anti-epithelial cell antibody (AECA) levels
 
Exploratory biomarkers (FCGR2A SNP, RNAseq, urine IgG)
 
Immune phenotyping by flow cytometry
 
 	Changes in CIC; C3; AECA levels by indirect immunofluorescence; FCGR2A SNP; RNAseq; urine IgG, CD3+CD4+ T, CD3+CD8+ T, monocytes, NK cells and B cells; urine IgG levels; changes in blood transcriptome	
  
	Objective	Endpoint	Primary		Safety and tolerability of 5 once-weekly IV infusions of SYNT001 to subjects with pemphigus vulgaris or foliaceus	AEs and clinical (safety) laboratory tests	Secondary		PK of SYNT001 following a 1-hour IV infusion	PK parameters: $t_{1/2}$ , $C_{max}$ , $T_{max}$ , $AUC_{0-24}$ , and $AUC_{0-\infty}$ .	Effect of 5 once-weekly IV doses of SYNT001 on: 
 
Total IgG (IgG1-4), IgA, IgM, and albumin
 
Serum anti-Dsg (1 and 3) antibodies
 
	Changes in levels of IgG, IgG subtypes (IgG1-4), IgA, IgM, albumin, serum anti-Dsg (1 and 3) antibodies	Assess immunogenicity	Anti-SYNT001 antibodies	Disease Activity	PDAI Scores	Exploratory		Effect of 5 once-weekly IV doses of SYNT001 on biomarkers including: 
 
CIC
 
C3
 
Serum anti-epithelial cell antibody (AECA) levels
 
Exploratory biomarkers (FCGR2A SNP, RNAseq, urine IgG)
 
Immune phenotyping by flow cytometry
 
	Changes in CIC; C3; AECA levels by indirect immunofluorescence; FCGR2A SNP; RNAseq; urine IgG, CD3 + CD4 + T, CD3 + CD8 + T, monocytes, NK cells and B cells; urine IgG levels; changes in blood transcriptome
Objective	Endpoint																				
Primary																					
Safety and tolerability of 5 once-weekly IV infusions of SYNT001 to subjects with pemphigus vulgaris or foliaceus	AEs and clinical (safety) laboratory tests																				
Secondary																					
PK of SYNT001 following a 1-hour IV infusion	PK parameters: $t_{1/2}$ , $C_{max}$ , $T_{max}$ , $AUC_{0-24}$ , and $AUC_{0-\infty}$ .																				
Effect of 5 once-weekly IV doses of SYNT001 on: 
 
Total IgG (IgG1-4), IgA, IgM, and albumin
 
Serum anti-Dsg (1 and 3) antibodies
 
	Changes in levels of IgG, IgG subtypes (IgG1-4), IgA, IgM, albumin, serum anti-Dsg (1 and 3) antibodies																				
Assess immunogenicity	Anti-SYNT001 antibodies																				
Disease Activity	PDAI Scores																				
Exploratory																					
Effect of 5 once-weekly IV doses of SYNT001 on biomarkers including: 
 
CIC
 
C3
 
Serum anti-epithelial cell antibody (AECA) levels
 
Exploratory biomarkers (FCGR2A SNP, RNAseq, urine IgG)
 
Immune phenotyping by flow cytometry
 
	Changes in CIC; C3; AECA levels by indirect immunofluorescence; FCGR2A SNP; RNAseq; urine IgG, CD3 + CD4 + T, CD3 + CD8 + T, monocytes, NK cells and B cells; urine IgG levels; changes in blood transcriptome																				

 
• Exploratory biomarkers to investigate immune response associated with pemphigus
 
	
Concomitant Treatment	Corticosteroid use during the study
SYNT001 levels in skin biopsies	Measures of SYNT001 levels in skin biopsies

Treatment-emergent AEs (TEAEs) will be summarized using the Medical Dictionary for Regulatory Activities (MedDRA®; Version 19 or higher) System Organ Class (SOC) and preferred term, classified from verbatim terms. The incidence and percentage of subjects with at least 1 occurrence of a preferred term will be included, using the most severe grade. The number of events per preferred term will also be summarized. Causality (relationship to study treatment) will be summarized separately.

TEAEs, SAEs, and AEs leading to withdrawal, or treatment discontinuation will be listed by subject, and cohort using SOC and preferred terms. Duration of AEs will be determined and included in listings, along with action taken, and outcome.

Laboratory results will be summarized by time point and cohort. The incidence of laboratory abnormalities will be summarized. The worst on-study grade after the first dose of study drug will be summarized. Results for variables that are not coded will be presented in the listings as below, within, and above the normal limits of the central laboratory. Vital sign measurements will be summarized by cohort at each scheduled time point using descriptive statistics.

Study drug concentrations will be used to calculate the following PK parameters:  $t_{1/2}$ ,  $C_{max}$ ,  $T_{max}$ , and area under the curve (AUC). PK parameters will be determined using non-compartmental method(s). Descriptive statistics of PK parameters for SYNT001 will include mean, standard deviation (SD), coefficient of variation (CV), median, minimum, and maximum.  $T_{max}$  will be reported as median and range. All descriptive statistics will be performed on untransformed PK parameters and after  $\log_{10}$  transformation of PK parameters.

PD results will be summarized by cohort. Descriptive statistics of PD parameters for SYNT001 will include mean, SD, CV, median, minimum, and maximum.

Immunogenicity results will be summarized by cohort. Descriptive statistics will include mean, SD, CV, median, minimum, and maximum.

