Methodology	
Two cohorts of 8 eligible subjects each will receive 5 once-weekly 60-minute infusions of SYNT001 in planned doses of 10 mg/kg or 30 mg/kg. Based on review of safety, PD, and clinical outcomes of these 2 cohorts, a third cohort of up to 8 subjects may be treated at another dose, with a maximum dose of 45 mg/kg, but may also be lower than 10 mg/kg or between 10 and 30 mg/kg, inclusive.
 
  
 Cohort	No. of subjects	Dose	
   
 1	8	SYNT001 10 mg/kg	
 
 2	8	SYNT001 30 mg/kg	
  
 
Cohorts will be dosed sequentially beginning with Cohort 1. The first 2 subjects will be dosed at least 24 hours apart. A review of the 24-hour safety data for the first subject will be performed to ensure that there are no overt safety concerns before dosing the second subject. A review of the 7-day safety data for the first 2 subjects will be performed prior to dosing the remaining 6 subjects in the cohort. This evaluation will include a review of AE/SAE reports, vital sign assessments, physical examinations, ECGs, and clinical laboratory testing. The seriousness, severity, and relatedness of AEs/SAEs will also be considered in the safety evaluation. Safety data will be reviewed on a continuous basis throughout the study. All safety data and any available and relevant PD data through Day 42 (2 weeks after the last subject's last dose in Cohort 1) will be reviewed by a dose escalation committee before Cohort 2 is initiated. Escalation to Cohort 2 will proceed if there are no concerning safety signals and the review of available and relevant PD data supports advancing to a higher dose. The dose for Cohort 2 will be finalized after review of the safety and PD data, but will not exceed 30 mg/kg. Cohort 2 and Cohort 3, if added, will be dosed per the same schedule as Cohort 1.
 
On days where study drug is administered, vital sign and pulse oximetry measurements will be collected immediately prior to the infusion; 15, 30, and 45 minutes after the start of the infusion; at completion of the infusion; and 30 minutes, 1 hour and 2 hours following completion of the infusion.
 
On Days 0 and 28, PK blood samples will be collected prior to infusion start and then over the subsequent 48 hours. Subjects will remain at the clinic through the
	Cohort	No. of subjects	Dose	1	8	SYNT001 10 mg/kg	2	8	SYNT001 30 mg/kg

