#### 3.2 Secondary Objectives

The secondary objectives of this study are as follow:

- To determine the PK of SYNT001 following 5 once-weekly 1-hour IV infusions at different dose levels
- To assess the effect of 5 once-weekly doses of SYNT001 at different dose levels on the following PD biomarkers:
  - Immunoglobulins: IgG, IgG subtypes (IgG1-4), IgA, IgM
  - Albumin
- To assess the effect of 5 once-weekly doses of SYNT001 at different dose levels on the following disease activity markers:
  - Serum anti-desmoglein (Dsg) (1 and 3) antibody levels
  - Pemphigus Disease Area Index (PDAI)
- To assess immunogenicity (anti-SYNT001 antibodies)

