### 6.7.6 Immunogenicity Testing

Serum samples will be collected for immunogenicity analyses on Days 0 (pre-dose), 14, 28, 56, 84 and 112.

SYNT001 is being developed for the acute and chronic therapy of autoimmune disorders. Although SYNT001 is a humanized IgG4 monoclonal antibody, exposure to SYNT001 in clinical trials could result in the development of anti-drug antibodies (ADAs), with potential consequences ranging from neutralization or lessening of drug efficacy to safety consequences such as allergic reactions. Testing will first detect binding ADAs, then, for all confirmed positive samples, there will be testing for neutralizing effects.

Detailed instructions for sample collection and preparation will be provided in a separate laboratory manual.

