### 12.1 General Design

All data for enrolled subjects will be presented in data listings by subject number.

Continuous data will be described using descriptive statistics: number of observations (n), mean, standard deviation (SD), median, minimum, and maximum. Frequencies and percentages will be used for summarizing discrete (categorical) data. When categorical data are presented, the percent will be suppressed when the count is zero to draw attention to the non-zero counts. The denominator for all percentages, unless otherwise specified, will be the number of subjects in the specified analysis population.

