## **12.7 Immunogenicity Data**

Immunogenicity results will be summarized by cohort.

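### The synopsis prescribes mean, SD and CV for an anti-drug antibody result that is positive or negative, against the protocol's own rule for categorical data

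*Protocol*

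**What the plan says.** Immunogenicity is a secondary objective in Section 3.2: "To assess immunogenicity (anti-SYNT001 antibodies". Section 6.7.6 sets the sampling: "Serum samples will be collected for immunogenicity analyses on Days 0 (pre-dose), 14, 28, 56, 84 and 112". The same section describes the test: "Testing will first detect binding ADAs, then, for all confirmed positive samples, there will be testing for neutralizing effects". It mentions no titre or concentration for ADA.

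The analysis is described in three places:

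- **Synopsis, Statistical methods:** "Immunogenicity results will be summarized by cohort. Descriptive statistics will include mean, SD, CV, median, minimum, and maximum". The preceding paragraph gives the same list for the pharmacodynamic (PD) parameters. The sentence also stands in the preceding protocol version in the file, so it came through an amendment unchanged.
- **Section 12.7:** "Immunogenicity results will be summarized by cohort". No statistics are named.
- **Section 12.1, the general rule:** "Frequencies and percentages will be used for summarizing discrete (categorical) data", with this default: "The denominator for all percentages, unless otherwise specified, will be the number of subjects in the specified analysis population".

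**The concern.** The statistics fixed in the synopsis are those for a quantitative measurement. They suit the PD levels, where the list probably comes from. They do not suit a confirmed positive/negative call followed by a second positive/negative call. For other event-type results (adverse events, laboratory abnormalities) the synopsis does name an incidence, but for ADA it does not.

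What is at stake is a readable result for a secondary objective. Section 6.7.6 itself says that ADA could neutralize the drug, lessen its effect or lead to allergic reactions. According to Section 2.2, the completed human study gave single doses, whereas this trial gives five weekly infusions. The useful findings are how many subjects become positive, when, and whether the antibodies neutralize. A table built literally from the synopsis sentence would show none of these clearly.

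**Working it through.** The protocol states no expected ADA rate and no sample size, power or precision for immunogenicity, so there is no figure of its own to reproduce. The check is whether the six synopsis statistics carry the information when applied to the result that Section 6.7.6 yields.

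**Inputs**

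- Cohort size n = 8, from the synopsis: "Two cohorts of 8 eligible subjects each will receive 5 once-weekly 60-minute infusions".
- Result per subject: positive = 1, negative = 0. This coding is an assumption; the protocol defines none.
- Number of positives x: assumed, and varied.

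**Formulas**, with p = x/n

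- Mean = p
- SD = √[n·p(1 − p)/(n − 1)]
- CV = SD/mean = √[n(1 − p)/((n − 1)p)]

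For x = 1: mean = 1/8 = 0.125. SD = √[8 × 0.125 × 0.875/7] = √0.125 = 0.354. CV = 0.354/0.125 = 283%.

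| Positives of 8 | Mean | SD | CV | Median | Min | Max | Count and % | Exact (Clopper-Pearson) 95% CI |
|---|---|---|---|---|---|---|---|---|
| 0 | 0 | 0 | undefined | 0 | 0 | 0 | 0 (0%) | 0 to 36.9% |
| 1 | 0.125 | 0.354 | 283% | 0 | 0 | 1 | 1 (12.5%) | 0.3 to 52.7% |
| 2 | 0.250 | 0.463 | 185% | 0 | 0 | 1 | 2 (25%) | 3.2 to 65.1% |
| 3 | 0.375 | 0.518 | 138% | 0 | 0 | 1 | 3 (37.5%) | 8.5 to 75.5% |
| 4 | 0.500 | 0.535 | 107% | 0.5 | 0 | 1 | 4 (50%) | 15.7 to 84.3% |

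**Reading the table**

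1. SD and CV depend only on p and n, so they add nothing to the proportion. The CV falls as more subjects become positive, and it does not exist when nobody does.
2. Median, minimum and maximum cannot tell 1 positive from 2 or 3.
3. The mean does equal the incidence, but only under a 0/1 coding that the protocol does not state.
4. The count and percentage column is what Section 12.1 gives for these data.

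**The case against.** The strongest reply is that the protocol already secures the right summary. If ADA status is categorical, Section 12.1 applies and yields frequencies and percentages. Section 12.7, in the body of the statistical section, does not repeat the continuous list. The synopsis says only what the statistics will include, which does not rule out counts. Section 12 promises listings of all clinical data, so with 8 subjects per cohort and six sampling days the reader could see who turned positive and when. Section 12.3 leaves detailed methods to the statistical analysis plan (SAP), which is not at hand and may modify the protocol's plan.

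All of this stands against the stronger reading that a reader might draw, namely that the planned statistics cannot answer the immunogenicity objective. The documents do not support that. It would also be wrong to show the size of the problem with a mean titre in which negatives count as zero, because the protocol names no ADA titre and no such coding. Exact confidence intervals and the finer definition of treatment-emergent ADA are optional or SAP matters, and their absence is no fault here.

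The reply does not remove the mismatch. The protocol has not simply left the matter open: it makes a specific choice, and that choice disagrees with Section 12.1. Under Section 12.3, an SAP that departs from the protocol's plan has to describe and justify the departure, which correcting the sentence avoids. Listings let a reader count, but they are not a planned summary.

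**Conclusion.** The point holds as a mismatch within the protocol. The synopsis prescribes continuous-variable statistics for a result that Section 6.7.6 makes categorical, and this conflicts with Section 12.1. The size is modest. One secondary objective would be summarized in a form that is undefined at 0/8 (CV), misleading at 1/8 (CV 283%) and partly uninformative between 1/8 and 3/8 (same median, minimum and maximum). These figures rest on an assumed 0/1 coding and assumed numbers of positives. If the laboratory also reports titres, continuous statistics have a proper use for those values, but the protocol does not say that it does. The primary safety objective, the dose-escalation rules, the sample size and the error rates are not affected.

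**What to change.** Replace the synopsis sentence, and align Section 12.7 with it, along these lines: for each cohort, the number and percentage of subjects with confirmed ADA, and with neutralizing ADA, at each sampling visit (including Day 0) and overall after baseline. State the denominator. Limit continuous summaries (median and range) to titres in positive subjects, if titres are measured. Exact 95% confidence intervals may be added but are not required.

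The cost is about one sentence in each of two places. No new samples, assays or visits are needed.

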**Table 1: Study Assessments**

Timepoint (Study Day)	Screening	Treatment Period															Follow-Up	
	-14 to -1	0	1 (±1 hr)	2 (±2 hr)	5 p (±4 hr)	7 (±6 hr)	12 p (±6 hr)	14 (±6 hr)	19 p (±6 hr)	21 (±6 hr)	28 (±6 hr)	29 (±1 hr)	30 (±2 hr)	33 (±4 hr)	42 (±3 days)	56 (±5 days)	84 (±5 days)	112 (±5 days) or ET Visit
Informed Consent	X																	
Demographics/Medical History	X																	
Inclusion/Exclusion	X																	
Physical Examination a	X	X				X		X		X	X				X	X	X	X
Vital Signs b	X	X	X	X	X	X	X	X	X	X	X	X	X	X	X	X	X	X
Pulse Oximetry c		X				X		X		X	X							
Clinical Safety Labs d	X	X				X		X		X	X			X	X	X	X	X
Pregnancy test e	X	X														X		X
Hepatitis & HIV Screen	X																	
12-Lead ECG f	X	X					X				X					X		
Tetanus & VZV antibodies		X														X	X	X
PDAI Score		X				X		X		X	X			X	X	X	X	X
PK Sampling h		X	X	X	X					X	X	X	X	X				
Immunogenicity i		X						X		X	X					X	X	X
Study Drug Administration j		X				X		X		X	X							
Immunoglobulins (IgG, IgA, IgM) and IgG subtypes (IgG 1-4) k	X	X	X	X	X	X	X	X	X	X	X	X	X	X	X	X	X	X q
CIC		X			X	X	X	X	X	X	X			X	X	X	X	X
Anti-Dsg (1 & 3) antibody titer	X	X				X		X						X		X	X	X
C3 and AECA l		X						X						X		X	X	X
FCGR2A m by buccal swab		X																
RNAseq m		X						X						X		X	X	X
Urine IgG m		X						X						X		X	X	X
Immune phenotyping n		X								X						X		
Pemphigus immune response biomarkers		X			X	X	X	X	X	X	X			X	X	X	X	X
Optional Skin Biopsy		X	X	X				X						X		X	X	
Photography o		X												X		X	X	X
Adverse Events	To be collected from the date that the ICF is signed through the last study visit																	
Concomitant Medications	To be collected from within 14 days prior to Day 0 through the last study visit																	

ECG = electrocardiogram; ET= Early Termination; HIV = human immunodeficiency virus; ICF = informed consent form; PD = pharmacodynamic; PK = pharmacokinetic; VZV = varicella-zoster virus

- a: Complete **PE**, including weight, to be performed. Height and BMI will be additional assessments conducted at screening.
- b: **Vital sign** measurements (sitting blood pressure, heart rate, respiratory rate, and oral temperature) to be obtained after 5 minutes of seated rest. Any abnormal measurements are to be repeated after 5 minutes of rest. On Days 0, 7, 14, 21, and 28 vital sign measurements will be collected immediately prior to the infusion; 15, 30, and 45 minutes after the start of the infusion; at completion of the infusion; and 30 minutes, 1 hour and 2 hours following completion of the infusion.
- c: **Pulse oximetry**: On Days 0, 7, 14, 21, and 28, pulse oximetry to be measured immediately prior to the infusion; 15, 30, and 45 minutes after the start of the infusion; at completion of the infusion; and 30 minutes, 1 hour and 2 hours following completion of the infusion.
- d: **Clinical safety labs**: hematology, clinical chemistry, and urinalysis (see [Section 6.7](#) for a complete list). Full clinical safety lab draws will be collected at Screening and on Days 0, 7, 14, 21, 28, 33, 42, 56, 84 and 112.
- e: **Pregnancy test**: To be performed at time of screening and prior to first dose of SYNT001 on Day 0 and on Days 56 and 112 (urine or serum test is acceptable, however, positive urine tests must be confirmed with serum testing.)
- f: Digital 12-lead **ECG** to be obtained after 5 minutes of rest in the supine position and in triplicate at least 1-2 minutes apart (see [Section 6.6](#) for additional information). On Days 0 and 28 to be obtained 5 minutes after the completion of infusion. Day 12 ECG will be collected only if the visit is conducted at the study site.
- g: **Serology**: Testing at Day 56 will not be done for any subject whose baseline titer is below the level of detection. If the Day 56 results are greater than 30% below the baseline value, or if the subject falls below the level of detection, the subject will be re-tested at Day 84; if still below the baseline value (or level of detection), the subject will be re-tested at Day 112. Any subject whose baseline value for tetanus or VZV was above the detectable level at baseline, and is not within 30% of the baseline value or is below the detectable level by Day 112, will be referred to their primary care physician for further management. See [Section 6.7.3](#) for additional information.
- h: **PK**: Starting on Days 0 and 28, serum samples will be collected just prior to the start of study drug infusion (pre-dose), and at 5 minutes and 2, 4, 6, 24, and 48 hours after the end-of-study drug infusion. Additional samples will be collected on Days 5 and 33. See [Section 6.7.4](#) for additional information.
- i: **Immunogenicity**: Blood samples will be collected pre-dose when collected on dosing days. Samples will be collected on Days 0, 14, 28, 56, 84 and 112. See [Section 6.7.6](#) for additional information.
- j: Prior to **study drug infusion**, SYNT001 drug product is to be diluted in Dextrose 5% in Water (D5W) to a total volume of 250 mL and administered intravenously over 1 hour using a 0.2-micron, inline filter. See [Section 9](#) for additional information.
- k: **Immunoglobulins (IgG, IgA, IgM) and IgG subtypes (IgG 1-4)**: Collected for measurements of IgG, IgG subtypes (IgG1-4), IgA, and IgM at every visit. On Days 0, 7, 14, 21, and 28, samples are collected prior to infusion of study drug. See [Section 6.7.5](#) for additional information
- l: Exploratory PD samples (C3 and AECA): collected pre-dose when collected on dosing days. See [Section 6.7.5](#) for complete information.
- m: Buccal samples to be collected and stored; pending review of clinical and pharmacodynamics assessments
- n: Immune phenotyping by flow cytometry for measurement of CD3+CD4+ T, CD3+CD8+ T, monocytes, NK cells and B cells
- o: Photographs of active lesions taken prior to first dose on Day 0. Follow-up photographs will be taken at Days 33, 56, 84 and 112. Subjects who begin a steroid taper will have additional photographs taken at the clinic visit during which the decision to begin the taper is made.
- p: Visit Days 5, 12 and 19 may be conducted via at-home nursing in lieu of a subject visit to the study site.
- q: Subjects will return to the clinic on Days 84 and 112 for follow-up visits. Subjects whose total IgG is not within 30% of their Day 0 baseline value and not above 500 mg/dL at the Day 112 visit will be referred for further management.

